9 DATA MANAGEMENT

9.1 Data Collection and Processing

Data will be collected in a secure, password protected electronic data capture (EDC) system, which is accessible via the Internet. All pertinent data will be entered by trained study center personnel into the electronic Case Report Forms (eCRFs). A unique subject ID number will be assigned to each subject enrolled. Every reasonable effort should be made to complete data entry within one week of data collection. Any data discrepancies may be queried during ongoing review of data by the sponsor or may be identified and queried during the routine remote monitoring process. Remote monitoring may be performed to verify data accuracy and ensure queries are resolved. The Principal Investigator must ensure the accuracy and completeness of the recorded data and provide his/her electronic signature on the appropriate eCRF.

If images are sent to a Core Lab, the results may also be entered into the EDC system and electronically signed by the reviewer responsible for entering this data. Ongoing data review will be performed to identify

Stryker Neurovascular

Document Title: ASSIST™ Registry Protocol

Document Number: CDM10001414

Rev: AB

possible data discrepancies. Manual and/or automatic queries will be created in the EDC system and will be issued to Core Lab for appropriate resolution.

10 MONITORING

Stryker Neurovascular will assess each participating site to assure that the Investigator(s) understand the protocol, as well as their obligations to conduct the Registry in accordance with applicable Regulations, GCP's and the Registry protocol. The monitor will also confirm that the Investigator has an adequate subject population, facilities, personnel and time to conduct the Registry properly. While the Sponsor intends to use remote monitoring methods, periodic on-site monitoring visits will be made to confirm that the site remains compliant with the protocol, applicable regulations, GCP and that all agreed-upon activities are carried out by the Investigator and other specified staff members.

Data will be monitored on-site and/or remotely for completeness and logical consistency. De-identified procedure summary and ASSIST Registry worksheets sent to Stryker Neurovascular must have the subject identification number recorded on any forms. The procedure documents for each subject enrolled may be compared against the eCRFs to ensure consistency.

It is important that the Investigator and relevant study site personnel are available during monitoring visits and that sufficient time is devoted to the process. In order to perform her or his role well, the monitor must be given access to primary subject medical records which support the Registry eCRFs. This access must be disclosed to the subject via the informed consent.

11 AUDITING

Sites may be subject to a quality assurance audit by Stryker Neurovascular or its designees, or other regulatory authorities.

12 ADVERSE EVENTS

An Adverse Event (AE) is any untoward medical occurrence, unintended disease or injury, or untoward clinical sign (including abnormal laboratory findings) in subjects, users or persons, whether or not related to the medical device(s). All subjects will be assessed for complications or adverse events during the procedure and at all follow-up visits per section 7.4-7.7, and recorded on the AE case report form. Data to be collected will include the AE event term, onset and resolution dates (or whether the AE is ongoing), seriousness, management/treatment, outcome, and determination of the relationship to the devices and the index procedure. All AEs will be followed until resolution or an appropriate endpoint is reached, or until the subject has completed or discontinued the registry.

More specifically, the following adverse events are to be reported on the Adverse Event case report form:

- All AEs and serious adverse events (SAE) that occur during the procedure
- Only device and/or procedure related AEs post procedure through Day 90
- All SAEs post procedure through Day 90

STRYKER CONFIDENTIAL - THIS DOCUMENT CONTAINS CONFIDENTIAL AND PROPRIETARY INFORMATION THAT IS THE PROPERTY OF STRYKER CORPORATION. NEITHER THIS DOCUMENT NOR THE INFORMATION HEREIN MAY BE REPRODUCED, USED, OR DISCLOSED TO ANY THIRD PARTY WITHOUT THE PRIOR WRITTEN CONSENT OF STRYKER CORPORATION.

Stryker Neurovascular

Document Title: ASSIST™ Registry Protocol

Document Number: CDM10001414

Rev: AB

NOTE: Any “prolonged” hospitalization(s) related to the study procedure which is considered standard of care due to subject age, co-morbidities or neurological status at presentation will not be considered SAEs

- Any event causing neurological deterioration defined as a ≥ 4 point increase on the NIHSS from baseline (e.g. cerebral edema, brain herniation, stroke progression) which is related to the index stroke
- Any event causing symptomatic intracranial hemorrhage (SICH) defined as a ≥ 4 point increase in NIHSS from baseline for which the hemorrhage is determined to be the cause
- All device-related adverse events (also known as “adverse device effects” [ADEs])
- All serious adverse device effects (SADEs)
- All unanticipated serious adverse device effects (USADEs)
- All adverse events that result in death through Day 90

NOTE: Death should not be recorded as the AE term but should be reflected as an outcome to a specific AE

Pre-treatment findings and pre-existing medical conditions will not be reported as AEs unless there is an increase in their frequency or severity during the course of the registry. Elective/planned hospitalization after enrollment in the Registry will not be regarded as an AE or a SAE. However, AEs that may occur during elective hospitalization, and are unrelated to the elective hospitalization should be evaluated and recorded appropriately.

Stryker Neurovascular

Document Title: ASSIST™ Registry Protocol

Document Number: CDM10001414

Rev: AB

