12.1 Adverse Event Definitions and Classification

Term	Definition	Reference
Adverse Event (AE)	Any untoward medical occurrence, unintended disease or injury, or untoward clinical signs (including abnormal laboratory findings) in a subject, users or other persons, whether or not related to the investigational medical device	ISO 14155:2011
Adverse Device Effect (ADE)	
Any adverse event related to the use of a medical device.
 
Note 1: This definition includes adverse events resulting from insufficient or inadequate instructions for use, deployment, implantation, installation, or operation, or any malfunction of the device.
 
Note 2: This definition includes any event resulting from use error or intentional misuse of the device
	ISO 14155:2011
Serious Adverse Event (SAE)	
An adverse event that:
 
• led to death, or• resulted in a life-threatening illness or injury, or• resulted in a permanent impairment of a body structure or a body function, or• required in-patient or prolonged hospitalization, or• resulted in medical or surgical intervention to prevent life-threatening illness or injury or permanent impairment to body structure or a body function, or• led to fetal distress, fetal death or a congenital abnormality or birth defect 
NOTE: Planned hospitalization for a pre-existing condition, or a procedure required by the protocol, without serious deterioration in health, is not considered a SAE
	ISO 14155:2011
Serious Adverse Device Effect (SADE)	An adverse device effect that has resulted in any of the consequences characteristic of a serious adverse event	ISO 14155:2011
Unanticipated Serious Adverse Device Effect (USADE)	Serious adverse device effect which by its nature, incidence, severity or outcome has not been identified in the current version of the risk analysis report	ISO 14155:2011

STRYKER CONFIDENTIAL - THIS DOCUMENT CONTAINS CONFIDENTIAL AND PROPRIETARY INFORMATION THAT IS THE PROPERTY OF STRYKER CORPORATION. NEITHER THIS DOCUMENT NOR THE INFORMATION HEREIN MAY BE REPRODUCED, USED, OR DISCLOSED TO ANY THIRD PARTY WITHOUT THE PRIOR WRITTEN CONSENT OF STRYKER CORPORATION.

Stryker Neurovascular

Document Title: ASSIST™ Registry Protocol

Document Number: CDM10001414

Rev: AB

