Pre-stroke disability: Obtained at baseline, but representative of the subject's status before the index stroke, assessed by mRS on medical history obtained from subject's medical chart, or family members.

Remote Intracerebral Hemorrhage (RIH): Any intraparenchymal hemorrhage remote from the ischemic field.

Serious Adverse Device Effect (SADE): Any serious adverse effect on health or safety or any life-threatening problem or death caused by, or associated with, a device, if that effect, problem, or death was not previously identified in nature, severity, or degree of incidence in the protocol or application (including a supplementary plan or application), or any other unanticipated serious problem associated with a device that relates to the rights, safety or welfare of subjects.

Serious Adverse Event (SAE): An adverse event in a research subject that led to a death, or led to a serious deterioration in the health of the subject that resulted in a life-threatening illness or injury, or resulted in a permanent impairment of a body structure or a body function, or required in-patient hospitalization or prolongation of existing hospitalization, or resulted in medical or surgical intervention to prevent permanent impairment to body structure or a body function. SAEs are a subset of AEs.

- NOTE 1 – This definition does not imply that there is a relationship between the serious adverse event and the device under investigation.
- NOTE 2 – Elective/planned hospitalization after the study procedure will not be regarded as an AE or a SAE. However, AEs that may occur during elective hospitalization, and are unrelated to the elective hospitalization should be evaluated and recorded appropriately.

Stryker Neurovascular

Document Title: ASSIST™ Registry Protocol

Document Number: CDM10001414

Rev: AB

Stroke: An acute neurological event with focal symptoms and signs lasting \geq 24 hours. Stroke can be sub-classified as Hemorrhagic or Ischemic.

- **Hemorrhagic Stroke:** A symptomatic intracerebral, subarachnoid, or primary intraventricular hemorrhage. To be considered a hemorrhagic stroke, the patient must experience new symptoms (e.g., new severe headache) that last for at least 24 hours (symptoms do not need to be associated with a new neurological deficit).
- **Ischemic Stroke:** A neurological deficit that is thought to have an ischemic cause and is detectable on examination at least 24 hours after onset of symptoms.

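### Section 12 and Appendix B exempt planned hospitalizations more widely than the SAE definition in Section 12.1, so some device- or procedure-related SAEs can be graded non-serious

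*Combined protocol and SAP*

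**What the plan says.** Three places in the protocol deal with planned admissions.

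- Section 12 (Adverse Events): "Elective/planned hospitalization after enrollment in the Registry will not be regarded as an AE or a SAE". It goes on to say that "AEs that may occur during elective hospitalization, and are unrelated to the elective hospitalization should be evaluated and recorded appropriately".
- Appendix B, SAE definition, Note 2: "Elective/planned hospitalization after the study procedure will not be regarded as an AE or a SAE". The same follow-on sentence about unrelated AEs appears there.
- Section 12.1, note to the SAE definition: "Planned hospitalization for a pre-existing condition, or a procedure required by the protocol, without serious deterioration in health, is not considered a SAE".

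Section 12.1 lists the seriousness criteria. They include an AE that "required in-patient or prolonged hospitalization" and, separately, one that "resulted in medical or surgical intervention to prevent life-threatening illness or injury or permanent impairment to body structure or a body function".

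The reporting list in Section 12 asks for "Only device and/or procedure related AEs post procedure through Day 90" and also for "All SAEs post procedure through Day 90". Neither item carries an exception for elective stays.

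Safety outcome 2 in Section 4.5 counts SAEs related to the device or the procedure up to Day 90. A related AE enters that outcome only if it is graded serious.

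**The concern.** The exemption in Section 12.1 is tied to the reason for the admission and to the absence of serious deterioration. Section 12 and Appendix B drop both conditions. Read literally, they set aside a scheduled admission made to treat a complication of the thrombectomy itself.

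Seriousness decides whether a related event counts in safety outcome 2. A rule that lets a site disregard one seriousness criterion can therefore lower that outcome. The effect would also depend on local habit, because a site that schedules repairs could grade the same complication differently from one that treats it urgently. Section 4 says registry data may support regulatory submissions, so a single rule matters.

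A second strand is the recording of AEs that occur during an elective stay. Asking only for unrelated ones suggests that related ones may be left out, which does not sit with a list that asks for all SAEs.

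**Working it through.** No arithmetic applies; the check is a comparison of the texts.

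**Step 1. The three exemptions side by side**

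| | Section 12 | Appendix B, Note 2 | Section 12.1 note |
|---|---|---|---|
| Reason for admission | any, if elective or planned | any, if elective or planned | existing condition, or protocol procedure |
| Condition on health | none | none | no serious deterioration |
| Status removed | AE and SAE | AE and SAE | SAE only |
| Counted from | enrollment | study procedure | not stated |

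The first two are wider than the third on reason, on health condition and on status removed. They also start at different times. Inclusion criterion 3 and Section 7.1 allow consent before the procedure or up to 48 hours after it, so enrollment and procedure need not coincide.

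**Step 2. One event under each rule**

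Take an illustrative case: an access-site pseudoaneurysm caused by the index procedure, found on Day 12 and repaired at a scheduled admission on Day 16. Appendix B itself lists pseudoaneurysm needing surgical repair among access-site complications.

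1. Is it reportable? Yes. It is a procedure-related AE before Day 90, and that reporting item does not depend on seriousness.
2. Is it serious under Section 12.1? Yes. It needed an in-patient stay. The exemption does not apply, because the condition is new and the repair is not a protocol procedure.
3. Is it serious for a site following Section 12 or Appendix B? If the site sets the planned admission aside, the answer rests on the other criteria. If the repair is judged to have prevented a threat to life or permanent impairment, the event is still an SAE under Section 12.1. If no other criterion is met, it is recorded as a non-serious AE.
4. Does it count in safety outcome 2? Yes under Section 12.1. No under the last branch of item 3.

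The gap is therefore confined to related AEs treated at a scheduled admission and meeting no other seriousness criterion. The remaining criteria are also not identical. Section 12.1 covers intervention to prevent life-threatening illness or permanent impairment, whereas Appendix B covers intervention to prevent permanent impairment only. A site working from Appendix B has a slightly weaker backstop.

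**Step 3. AEs during an elective stay**

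The follow-on sentence creates a duty to record unrelated AEs and is silent on related ones. The reporting list asks for all SAEs through Day 90 without exception. The two conflict by implication: a site could rely on the first to omit an SAE that the second requires.

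**Step 4. Size and direction**

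The documents give no share of complications treated by planned readmission. The nearest figure is the 5.0% device-related SAE rate of the TREVO study in Section 2.1, which with 60 subjects is 0.05 × 60 = 3 events. It excludes events related only to the procedure and says nothing about how events were treated, so no undercount can be derived from it. The direction does follow from the logic: disregarding a criterion can move an event from serious to non-serious, never the other way.

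**The case against.** The strongest reply is that these sentences concern the hospitalization, not the AE that led to it. A scheduled stay is not an event, and saying so does not make the underlying complication any less serious. The Section 12 sentence also follows directly on one about pre-existing conditions, so it can be read as meant for stays unconnected with the stroke treatment. Every related AE remains reportable, and seriousness and management are recorded for each. Repair of a complication will often meet the intervention criterion anyway. To lose an event from the outcome, a site must regard treatment of a new complication as elective or planned, let Section 12 or Appendix B override Section 12.1, and find no other criterion met.

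Most of this stands, and it limits the point to a narrow subset. It does not remove the conflict. The narrower reading of Section 12 has to be supplied by the reader, since the sentence itself sets no limit on the reason for admission. Nor does the protocol describe a body that re-grades seriousness after the site: the core lab adjudicates imaging, and the Steering Committee has general oversight.

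A reader might go further and infer that deaths or their causes could go missing, for example after a stroke during a planned later carotid admission. The documents do not support that. The Section 12 list separately requires every AE resulting in death through Day 90, and Sections 7.4 to 7.7 collect all deaths with available cause and date. A stroke caused by a later, separate procedure would also not ordinarily be related to the index procedure under Section 12.2, so it does not show a loss from safety outcome 2.

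**Conclusion.** The inconsistency is real and should be corrected. Section 12 and Appendix B Note 2 exempt more than the protocol's own SAE definition does, and they differ from each other on the starting point. The consequence is possible under-grading of device- or procedure-related AEs for which hospitalization is the only seriousness criterion and the admission was scheduled. Such events can be missed in safety outcome 2.

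This rests on one assumption: that some sites will apply the wider wording as written. The size of any undercount cannot be derived from the documents and could be zero; the direction is towards fewer SAEs.

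Two stronger readings are tempting. One is that procedure-related events drop out of the data altogether; they do not, because the AE stays reportable and only its grade is exposed. The other is that AEs related to an elective stay are expressly excluded; that is an inference from the wording, and no section states it.

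**What to change.** 1. In Section 12 and in Appendix B, SAE Note 2, replace the open exemption with the one in Section 12.1, keeping both of its conditions. This also removes the difference in starting point.
2. State in both places that a planned admission to treat an AE with onset during or after the index procedure meets the hospitalization criterion.
3. In both follow-on sentences, delete the clause that restricts recording to AEs unrelated to the elective stay. SAEs during planned stays are then reported like any other, with relationship to device and index procedure assessed under Section 12.2.

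The cost is a wording change in two places and a line in the eCRF completion guidance. Sites may file a few more SAE reports, and the reported SAE rate may be slightly higher.

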12.1 Adverse Event Definitions and Classification

Term	Definition	Reference
Adverse Event (AE)	Any untoward medical occurrence, unintended disease or injury, or untoward clinical signs (including abnormal laboratory findings) in a subject, users or other persons, whether or not related to the investigational medical device	ISO 14155:2011
Adverse Device Effect (ADE)	
Any adverse event related to the use of a medical device.
 
Note 1: This definition includes adverse events resulting from insufficient or inadequate instructions for use, deployment, implantation, installation, or operation, or any malfunction of the device.
 
Note 2: This definition includes any event resulting from use error or intentional misuse of the device
	ISO 14155:2011
Serious Adverse Event (SAE)	
An adverse event that:
 
• led to death, or• resulted in a life-threatening illness or injury, or• resulted in a permanent impairment of a body structure or a body function, or• required in-patient or prolonged hospitalization, or• resulted in medical or surgical intervention to prevent life-threatening illness or injury or permanent impairment to body structure or a body function, or• led to fetal distress, fetal death or a congenital abnormality or birth defect 
NOTE: Planned hospitalization for a pre-existing condition, or a procedure required by the protocol, without serious deterioration in health, is not considered a SAE
	ISO 14155:2011
Serious Adverse Device Effect (SADE)	An adverse device effect that has resulted in any of the consequences characteristic of a serious adverse event	ISO 14155:2011
Unanticipated Serious Adverse Device Effect (USADE)	Serious adverse device effect which by its nature, incidence, severity or outcome has not been identified in the current version of the risk analysis report	ISO 14155:2011

STRYKER CONFIDENTIAL - THIS DOCUMENT CONTAINS CONFIDENTIAL AND PROPRIETARY INFORMATION THAT IS THE PROPERTY OF STRYKER CORPORATION. NEITHER THIS DOCUMENT NOR THE INFORMATION HEREIN MAY BE REPRODUCED, USED, OR DISCLOSED TO ANY THIRD PARTY WITHOUT THE PRIOR WRITTEN CONSENT OF STRYKER CORPORATION.

Stryker Neurovascular

Document Title: ASSIST™ Registry Protocol

Document Number: CDM10001414

Rev: AB

12.2 Relationship

The Investigator must assess the relationship of the AE to each Stryker Neurovascular device using the following criteria categories and definitions:

- Unrelated - The AE is due to a concurrent illness or effect of another device/drug and is not related to the study device.
- Related - The AE is due to the study device (possible, probable, or highly probable).

All AEs that are related to a Stryker device will be reported to the Stryker Neurovascular Complaint Management Center prompting a further investigation. Sites will be contacted for more detailed information.

The Investigator must assess the relationship of the AE to the index procedure using the following categories and definitions:

- Unrelated - The AE is due to a concurrent illness or effect of a drug and is not related to the index procedure.
- Related - The AE is due to the index procedure (possible, probable, or highly probable).

12.3 Reporting Requirements

Any death or device and/or procedure related AEs and all SAEs should be reported within 24 hours of becoming aware to Stryker Neurovascular via data entry into the eCRFs. If access to eCRFs is not available, then the information can be emailed to [contact].

12.4 Device Failures, Malfunctions, and Product Nonconformities

All Stryker Neurovascular product failures, malfunctions and product nonconformities will be documented on the appropriate eCRF, and the involved device(s) should be returned to Stryker Neurovascular for analysis if possible. Assistance with returning the study device(s) can be provided by contacting your local Customer Service Center. Contact information for Customer Service Centers is located in the Regulatory Binder. Device failures and malfunctions should also be documented in the subject's medical record.

All Stryker Neurovascular device failures, malfunctions and product nonconformities should be reported within 24 hours of becoming aware to Stryker Neurovascular via data entry into the eCRFs. If access to eCRFs is not available, then the information can be emailed to [contact].

NOTE: Stryker Neurovascular device failures, malfunctions and product nonconformities should be reported as soon as possible after becoming aware of them and are not to be reported as adverse events. However, if there is an adverse event that results from a device failure or malfunction, that specific event would be recorded on the appropriate eCRF. All Stryker device failures, malfunctions, product nonconformities and resulting AEs are reported to the Stryker Neurovascular Complaint Management Center prompting a further investigation. Sites will be contacted for more detailed information.

Stryker Neurovascular

Document Title: ASSIST™ Registry Protocol

Document Number: CDM10001414

Rev: AB

